## **9. RESEARCH DESIGN AND METHODS**

The following research design applies to each of the following studies:

Sub-study 1a: FoTv vs. placebo for acute COVID-19 patients

Sub-study 1b: QFPD vs. placebo for acute COVID-19 patients

Sub-study 1c: FoTv vs. placebo as an adjunct to COVID-19 vaccination

Sub-studies 1a and 1b of Phase 1 trial will each be 2-arm multicenter double blind randomized placebo controlled clinical trials.

Each of these safety/feasibility sub-studies will be conducted identically with the exception of additional exclusion criteria that will be required for sub-study 1b on account of the presence of herbal components including ephedrine that require these precautions for avoiding herb-drug interactions.

Sub-study 1c will be a single site double blind randomized placebo controlled clinical trial.

This will be a shorter intervention with broader inclusion criteria.

The research design and methods for the larger efficacy trial (Phase 2) will require analysis of these first two feasibility studies, and the final protocol will be submitted as a future amendment.

The primary objective of sub-studies 1a and 1b will be to assess the safety of FoTv or mQFPD, respectively, when used as therapies for acute COVID-19 infection and feasibility of the study protocol.

The primary objectives of sub-study 1c will be to ascertain the safety of FoTv when used as an adjunct to standard COVID vaccination as well as to evaluate its effects on post-vaccine COVID-19 antibody titers and on vaccination-related side effects.

A total of 66 subjects (33 FoTv or mQFPD and 33 placebo) will be enrolled in each of the 1a and 1b sub-studies.

A total of 266 subjects (133 FoTv and 133 placebo) will be enrolled in sub-study 1c.

The study protocol will be implemented and safety, feasibility, clinical, and laboratory data will be collected.

Interested participants will be asked to contact the study team, who will then conduct screening, consenting, and study enrollment. The study will be open to patients who are

- a) Mildly-to-moderately symptomatic and have tested positive for COVID-19 (sub-studies 1a and 1b)
- b) Scheduled for COVID-19 vaccination (sub-study 1c).

See section 11 for recruitment plan.

Once their eligibility has been confirmed, participants will be randomized to one of two groups by the study statistician:

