#### **Exclusion Criteria**

1. Any of the following symptoms which, according to the CDC, require hospitalization:
  - a. Trouble breathing
  - b. Persistent pain or pressure in the chest
  - c. New confusion or inability to arouse
  - d. Bluish lips or face
2. Current use of investigational agents to prevent or treat COVID-19
3. Prisoners
4. Known liver disease (ALT/AST >3x ULN or diagnosis of cirrhosis)
5. Known renal disease (eGFR < 60 ml/min) or acute nephritis.
6. Uncontrolled hypertension (SBP>140 or DBP>90 while on medications)
7. Pregnant or breastfeeding women
8. Allergy to tree nuts
9. Bleeding dyscrasia or on anticoagulation (aspirin and/or clopidogrel is allowed)
10. Use of Tolbutamide
11. Use of systemic corticosteroids (hydrocortisone, cortisone, prednisolone, betamethasone, methylprednisolone, prednisone, dexamethasone). Inhaled budesonide is to be allowed.
12. Use of digoxin
13. Use of Oxacillin
14. Use of Interferon

15. Use of Vincristine
16. Use of Cyclosporine
17. Use of Amiodarone
18. Patients with a past medical history of epilepsy
19. Use of monoamine oxidase inhibitors (MAOI)
20. Use of Methamphetamine within the prior 30 days
21. Use of Cocaine within the prior 30 days
22. Use of aminoglycosides, carbamazepine, flecainide, lithium, phenytoin, phenobarbital, rifampicin, theophylline and warfarin

Sub-study 1c Fo-Tv vs. placebo:

266 total patients who are receiving COVID-19 vaccination will be included in the study.

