#### mQFPD risk

The modified Qing Fei Bai Du preparation is a blend of 21 total herbs. Please refer to Appendix 1.pdf which provides a detailed safety profile of each of the herbs which was completed with the help of [name]., Pharm.D., O.M.D., L.Ac. who is the author of "Chinese Medical Herbology and Pharmacology," a seminal textbook on Chinese herbal pharmacology. Each of the potentially negative herb-drug interactions listed in the document is reflected in the exclusion criteria and monitoring requirements.

As discussed above, a recent clinical trial of 98 patients using the complete 196g decoction dose of mQFPD daily for 9 days demonstrated the following adverse reactions: 4 patients developed symptoms of nausea and vomiting, 2 patients developed symptoms of dizziness, and 1 patient developed symptoms of rash. When reported as adverse reactions per total days of treatment, the incidence of adverse reactions was 0.07% (Wang 2020). By comparison, this trial will utilize an equivalent to 74.5g per day for 14 days.

1. Of note, three of the herbs in the original QFPD formulation have additional concerns that are addressed below. The herbs and concerns are addressed as follows.  
Ma Huang (Herba Ephedrae)
  - This herb has a long history of use in China as well as domestically for viral respiratory infection, part of which is attributed to the presence of ephedrine. Unfortunately, in the 1990s it became used in extracted forms as an OTC stimulant. Subsequently, the FDA restricted OTC sales to respond to

concerns of abuse potential, but it remains available to be prescribed domestically by licensed TCM practitioners.

- In consultation with the Study Team of TCM practitioners, this herb is of central medicinal value in the formula and cannot be replaced. The dosages of ephedrine used in this study will be far lower than they were in OTC extracted forms prevalent in the 1990s.

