- To ensure safety, concerns regarding drug-drug interactions and adverse events are addressed in the exclusion criteria as well as our safety monitoring as described in the protocol, which includes daily blood pressure measurements for hypertensive study participants. In addition, a certificate of analysis (COA) will be produced demonstrating specific quantities of ephedrine in the Ma Huang BRM. If the total daily ephedrine contained within 12g of mQFPD capsules exceeds the recommended maximum of 150mg per 24 hours, we will notify the FDA and amend the quantity of Ma Huang in the formula as appropriate.

2. Xi Xin (Radix et Rhizoma Asari): This herb is of concern due to the possibility of improper preparations which have contained Aristolochic acid (AA). Consequently, this herb has been restricted from importation by the FDA.

- In consultation with the study's panel of TCM practitioners, this herb is also of central medicinal value and cannot be replaced.
- To ensure proper safety standards, a certificate of analysis (COA) is attached demonstrating non-detectable quantities of AA by HPLC with tandem mass spectroscopy LC/MS/MS. This analysis was conducted on the specific batch of botanical raw material to be used in final production of study material.

3. Kuan Dong Hua (Flos Farfarae) is present in the original QFPD formula being used in China. This has been substituted with Pi Pa Ye (Folium Eriobotryae) for the purpose below:

- This herb (Flos Farfarae) contains pyrrolizidine alkaloids (PA) and may be linked to liver injuries. The FDA prohibits the use of herbs that contain PA.
- In consultation with the study's panel of TCM practitioners, this herb is not of central medicinal value and can be replaced. To avoid this issue of PA, this herb has been substituted with Pi Pa Ye (Folium Eriobotryae) in the research formulation.

This substitution requires the formula be renamed with the moniker modified QFPD, or mQFPD, to reflect the substitution of Kuang Dong Hua with Pi Pa Ye.

In addition to these concerns regarding specific herbs, Chinese medicine formulations in general have had a history of containing inappropriate amounts of heavy metals in the final protocol. For this reason, both the raw herbs and the final investigational product will be extensively tested and analyzed for heavy metals, the results to be included in the COA as specified in section 8.3.

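### Sub-study 1b limits ephedrine only through capsule content: no exclusion, avoidance instruction or concomitant-therapy rule in the protocol bars outside ephedra (Ma Huang) or ephedrine products

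*Combined protocol and SAP*

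**What the plan says.** Section 9 (Research Design and Methods) says 1a and 1b are run identically except for "additional exclusion criteria that will be required for sub-study 1b on account of the presence of herbal components including ephedrine". Section 14 (mQFPD risk) states that for Ma Huang "concerns regarding drug-drug interactions and adverse events are addressed in the exclusion criteria as well as our safety monitoring", and gives daily blood pressure in hypertensive participants as an example. It adds that each of the potentially negative "herb-drug interactions listed in the document is reflected in the exclusion criteria and monitoring requirements"; the document meant is Appendix 1, the herb safety profiles.

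The only numerical ephedrine limit is in the same section: "If the total daily ephedrine contained within 12g of mQFPD capsules exceeds the recommended maximum of 150mg per 24 hours", the FDA is told and the amount of Ma Huang in the formula is changed.

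On outside supply, Section 14 says that "the FDA restricted OTC sales to respond to" concerns about abuse, but that "it remains available to be prescribed domestically by licensed TCM practitioners". It describes a long history of Ma Huang use for viral respiratory infection. On dose it says: "The dosages of ephedrine used in this study will be far lower than they were in OTC extracted forms prevalent in the 1990s".

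The 1b exclusion list in Section 10 has 22 items. They include "Use of Methamphetamine within the prior 30 days", cocaine over the same period, MAOIs, theophylline, uncontrolled hypertension, and current investigational agents aimed at COVID-19.

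**The concern.** The protocol hands the ephedrine interaction risk to the 1b exclusions and to monitoring. The most direct ephedrine hazard, a second source of the same substance, appears in neither. The 150 mg check is a product specification. It can be met by every batch while a participant who also takes an outside Ma Huang formula exceeds that amount.

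An outside source is possible in this population. Participants have an acute viral respiratory infection, the indication for which the protocol says Ma Huang is traditionally used, and the protocol says practitioners can still prescribe it.

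What is at stake is participant safety in a sub-study whose primary objectives are safety and feasibility. A site that follows the list to the letter would admit a current ephedra user to an ephedrine-containing product, while turning away someone who used methamphetamine or cocaine in the past month.

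**Working it through.** This is mainly a comparison of texts, with a little arithmetic.

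**1. The capsule limit.** Inputs: 8 capsules three times a day (Section 9, Test Product Dose); 500 mg per capsule (Section 14, Brown Rice Placebo Risk; stated for the placebo and assumed equal for mQFPD).

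- 8 × 3 = 24 capsules per day
- 24 × 0.5 g = 12 g per day, which reproduces the 12 g in Section 14
- 150 mg ÷ 12,000 mg = 1.25% ephedrine by capsule mass at the limit

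The actual ephedrine content is not given. Room left for outside ephedrine before total intake passes 150 mg is 150 minus the capsule content:

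| Capsule ephedrine, mg/day (assumed range) | Room left, mg/day |
|---|---|
| 0 | 150 |
| 50 | 100 |
| 100 | 50 |
| 150 | 0 |

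No rule in the protocol controls what a participant takes within or beyond that room.

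**2. Where a bar could sit, and what is there.**

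| Place | Content | Names ephedra, Ma Huang or ephedrine? |
|---|---|---|
| Section 10, 1b exclusions | 22 items | 0 of 22 |
| Section 9, avoidance instruction; Section 10, 1b inclusion 5 | Alcohol, cannabis, dairy | 0 of 3 |
| Section 9, Concomitant Medications | Documentation at baseline/screening and Days 14, 28 and 58 | No; nothing is prohibited |

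**3. Would undeclared or later use be seen in time?** Medical History adds medication reconciliation at baseline and Day 1. The next scheduled record is Day 14, when the 14-day course is complete. Outside ephedra started after Day 1 may therefore be recorded only once exposure is over.

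The 1b diary, as described in Sections 6 and 9, collects symptoms, vitals, compliance and possible side effects. The package list mentions a medication diary, but the text uses it for missed study doses. The 1c diary does ask about other medication, although 1c does not use mQFPD.

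**4. Does monitoring cover the gap?** Under Vital Signs, home blood pressure is taken only by participants with a baseline diagnosis of hypertension. No other 1b participant has a scheduled blood pressure measurement there.

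**5. Size.** Only the mQFPD arm can be doubly exposed: 33 ÷ 66 = 50% at most. The other 33 take rice placebo.

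**The case against.** The strongest reply is that the absence is shown only for the protocol body. Every participant receives written product instructions, Appendix 1 profiles each herb, and the consent text was not available. A warning may sit in any of them. That stands as a limit on confidence. It is weakened by the protocol's own statement that the Appendix 1 interactions are carried into the exclusions and monitoring, where ephedra is not named.

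Second, a Ma Huang formula taken for COVID-19 might fall under the exclusion of investigational agents. This is arguable, but a herb described as open to ordinary prescription would not clearly be read as investigational, and the criterion acts at entry only.

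Third, dose. In the uncontrolled study of 98 patients cited in Section 14, the full 196 g/day decoction was taken for 9 days; reported reactions were nausea and vomiting (4), dizziness (2) and rash (1). Sub-study 1b uses the equivalent of 74.5 g/day, and 74.5 ÷ 196 = 38%. Doubling it gives 149 g, still below 196 g. This is fair context, but it compares formula weight rather than measured ephedrine, over a shorter course, and an outside product could be stronger.

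Fourth, other safeguards lower the consequence: baseline and Day 1 reconciliation, daily contact and symptom review, the 24-hour physician line, and the hypertension exclusion. They may reveal declared use or early effects. None prevents double exposure, and no written rule says what to do when outside ephedra is declared.

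Finally, no passage ties the methamphetamine and cocaine exclusions to ephedrine specifically. Reading them as ephedrine precautions is an inference from the general reason given in Section 9.

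**Conclusion.** The concern holds for the protocol text. Ephedrine intake is limited only through capsule content, and nothing in the eligibility, avoidance or concomitant-therapy rules bars a second source. It should be corrected, with medium confidence.

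The 33 of 66 is a ceiling, not an estimate. Likelihood cannot be quantified without the capsule content and the rate of outside use, and no passage shows that any participant would pass 150 mg. The conclusion assumes that the instructions, consent text and Appendix 1 contain no such bar. If they do, the remaining fault is that it is missing from the criteria that sites apply.

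**What to change.** - Add to the 1b exclusions in Section 10: *current use of ephedra/Ma Huang- or ephedrine-containing products, including Chinese herbal formulas that contain them*. Any washout is for the sponsor's clinicians to set.
- Add the same products to the avoidance instruction for 1b in Section 9.
- Ask about them by name at baseline.
- Carry the 1c diary question on other medication into the 1b diary, and send positive answers to the medical monitor.
- If the product instructions, consent text or Appendix 1 already bar ephedra, copy that wording into Sections 9 and 10.

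The cost is one exclusion line, one avoidance item and one diary question already in use, plus review of the amendment. A few more candidates may fail screening. Sample Size Justification plans about 90 screened to enroll 66, so 90 − 66 = 24 losses are already allowed for, counting those who decline as well as those found ineligible.

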#### **Inclusion Criteria**

1. Scheduled to receive COVID-19 vaccination
2. Age 18 and older

#### **Exclusion Criteria**

1. Current use of investigational agents to prevent or treat COVID-19
2. Prisoners
3. Known liver disease
4. Known renal disease or acute nephritis.
5. Pregnant or breastfeeding women
6. Use of immunosuppressive medication

### **11. RECRUITMENT AND PROCEDURES PREPARATORY TO RESEARCH**

Study participants will be recruited from COVID-19 testing sites, vaccination centers, UC, and other clinics. The 1a and 1b sub-studies will be open to patients who have received a positive COVID-19 diagnosis from CLIA certified and fully accredited COVID-19 testing laboratories and clinics. Sub-study 1c will be open to patients scheduled to receive vaccination at any vaccination centers or sites. Study participants will be asked to provide the contact information of their primary care physician so that the study team can contact them as needed.

#### **The following methods may be used to recruit potential participants:**

- (1) Dissemination of IRB-approved recruitment materials throughout dedicated COVID-19 testing sites and clinics throughout California that are local to or affiliated with each of the participating UC study sites. Interested participants will be directed to contact a dedicated phone number or email address. Participation will be open to all members of the community.
- (2) Review of medical charts for potential participant identification and selection. We will recruit participants from UC primary care patients who have screened positive for COVID-19 and meet other study eligibility criteria. Potential participants will be contacted via “MyChart” using the HRPP-approved recruitment flyer, or through their PCP using the same content. EPIC will be flagged and the physician will be notified via a secure email about their patient’s participation in this study. The study consent form will be uploaded to Epic via Media Manager
- (3) Use of the “ResearchMatch” platform
- (4) Use of social media to advertise the study using text from the HRPP-approved materials.

**Waiver of Documented Consent/HIPAA is requested for the purpose of aiding in research recruitment, identifying prospective research participants who meet the eligibility criteria for enrollment review**

### **12. INFORMED CONSENT**

A research coordinator will contact interested individuals to discuss the study details, answer any questions, and obtain informed consent orally. The consent document may also be emailed to the individual and then explained over the phone.

In order to minimize the risk of transmitting infection during the COVID-19 pandemic and best comply with safety recommendations and regulations, personal contact, as well as the back-and-forth mailing of physical documents, with COVID-19 infected patients must be avoided. Therefore, the process for obtaining appropriate procedural informed consent from patients' needs to be revised. Signed informed consent from the sub-studies 1a and 1b subjects will be collected using the UCSD DocuSign part 11 certified service application.

The study team may also use an alternate form of consent (as indicated in FAQ12 of the FDA's Conduct of Clinical Trials of Medical Products During the Covid-19 Public Health Emergency: Guidance for Industry, Investigators, and Institutional Review Boards, dated 1/27/21):

The consent form may be sent to the trial participant or their legally authorized representative by facsimile or email, and the consent interview may then be conducted by telephone when the trial participant or their legally authorized representative can read the consent form during the discussion. After the consent discussion, the trial participant or their legally authorized representative can sign and date the consent form. Options for returning the document to the clinical investigator may include facsimile, a photographic image sent through electronic means, scanning the consent form and returning it through a secure email account, posting it to a secure Internet address, or having it picked by a study team member.

Prior to any investigation-related procedures, documented informed consent from sub-study 1c participants will be obtained by the study team, after explaining the objectives of and procedures involved in this investigation.

#### **HIPAA Authorization waiver is requested for three reasons:**

- To facilitate recruitment (as described above)
- The PHI will be used for three discrete purposes: To identify COVID-19 patients with confirmatory test and have a means for direct communication within this narrow time window. Note that for those individuals who decline to participate, any identifying information will be destroyed.
- To collect end-of-study data from any patients that are hospitalized during their involvement in the study, in order to 1) compare admission laboratory evaluations to baseline laboratory evaluations to determine safety, and 2) provide sufficient data for an endpoint adjudication committee to determine if primary and secondary endpoints were met. This component is minimal risk because the data analysis will be done retrospectively and will not impact the medical care of the study participant.

The data gathered as described above will explicitly be used only for the purposes of this study and will not be used for marketing, recruitment, or shared with anybody outside of the authorized members of the study team. Once collected, PHI will be removed and replaced with a unique patient identifier for analysis. The PHI will only be reviewed by properly trained and authorized study team members. Only eligibility criteria will be accessed/reviewed.

The measures described elsewhere in this document to protect the privacy of study participants will also be applied to these data. As with any digital technology, even the most secure data networks are at times subject to compromise. However, this small risk is outweighed by the direct benefit to the study participant of having accurate prior laboratory data to confirm their safety.

We plan to:

- Protect identifiers from improper use and disclosure. The data will not be used as a part of the research data. Only properly trained and delegated study team members will be authorized to perform the screening/chart review.
- Destroy identifiers at the earliest opportunity or provide justification for retaining the identifiers. All identifiers will be destroyed immediately after reviewing the daily list with the doctor. No PHI will be stored or utilized, unless a potential subject has agreed to participate, consented and signed a HIPAA authorization to do so.

The PHI data will not be re-used or disclosed for other purposes

Subjects will be granted a copy of the final study publication on request.

### **13. ALTERNATIVES TO STUDY PARTICIPATION**

Sub-studies 1a and 1b:

The FDA has recently authorized co-administration of bamlanivimab and etesevimab for emergency use for the treatment of mild to moderate COVID-19 in adults who are at high risk for progressing to severe COVID-19 and/or hospitalization. Please be informed that this treatment option may be available to you, along with all other monoclonal antibody treatments authorized by FDA, as appropriate. Based on the totality of scientific evidence available, these therapies may be effective in reducing COVID-19 related hospitalization and/or deaths

Sub-study 1c: The alternative to participation in this study will be to not participate.

